8.8 Time Periods for Analyses

Some analyses will be performed by time period. For these analyses, the following definitions will be used:

- Screening Period (Switch subjects only) - from informed consent until the first dose of study drug
- Dose-Adjustment Period (Switch subjects only) – Baseline through Week 4
- Extended Dose-Adjustment Period (Switch subjects only) – Baseline through Week 8
- Titration Period (Rollover subjects only) – Baseline through Week 8
- Stable-Dose Period - from Week 8 through the last dose of study drug
- Entire Treatment Period - Baseline through last dose of study drug
- Follow-up Period - from the last dose of study drug through the end of the study

Subjects who withdraw from the study during the Titration Period or the Extended Dose-Adjustment Period will not have a Stable-Dose Period. For the analyses of adverse events, to be conservative, all follow-up adverse events will be counted as events that occurred during the last available treatment period prior to the Follow-up period.

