3.2 *Rationale for Study Design*

The study is designed to evaluate the long term safety and tolerability of SD-809 ER in subjects with chorea associated with HD. Two cohorts of subjects may enter the study: 1) Rollover subjects, who successfully complete the well-controlled efficacy study (SD-809-C-15) and 2) Switch subjects, who are receiving FDA-approved doses of tetrabenazine for treatment of chorea.

Given the two groups of subjects entering this trial have different background therapy at entry; identification of their optimal dose will be approached differently. Rollover subjects from Study SD-809-C-15 will have discontinued study medication (SD-809 ER or placebo) for at least one week and consequently they will begin dosing at 6 mg/day and titrate to their optimal dose level for up to 8 weeks. In contrast, Switch subjects will be on a stable dose of TBZ at entry and will make a direct conversion to SD-809 ER overnight based on their incoming TBZ regimen. As such, Switch subjects should reach their target dose more rapidly and they are allowed up to 4 weeks to adjust their SD-809 ER regimen after conversion. Although the time to reach an optimal dose may differ between these cohorts, both groups are expected to reach a pharmacologically active dose by two weeks: Rollover subjects would be at 12 mg/day, unless they experienced adverse events or adequate chorea control; and Switch subjects would have converted to a dose level that provides comparable exposure to their incoming tetrabenazine dose, with one intervening visit to evaluate/adjust dose level. Accordingly, the long term period of the study will be deemed to have started after two weeks of treatment even though dose adjustment may continue after this point.

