5.2.3 Dosing in Rollover subjects

The starting dose of SD-809 ER is 6 mg in the morning, regardless of previous treatment in the SD-809-C-15 trial. Treatment assignment (SD-809 ER or placebo) from SD-809-C-15 will remain blinded. Study drug will be titrated over the initial 8 weeks of therapy, if necessary, to identify a dose that provides adequate chorea control and is well tolerated. Changes in dose should not be made more often than once per week unless the subject is experiencing an intolerable adverse event. Additional dose adjustments may be made after week 8 if clinically indicated.

During the titration period, the dose of SD-809 ER may be increased on a weekly basis in increments of 6 mg per day (6 mg/day or 12 mg/day after a total daily dose of 48 mg is reached) until there is adequate control of chorea; the subject experiences a protocol defined “clinically significant” adverse event (defined as related to study medication and either a) moderate or severe in intensity or b) meets the criteria for a Serious Adverse Event [SAE])¹; or the maximal allowable dose is reached. If a subject experiences a “clinically significant” AE attributable to SD-809, the investigator will determine if a dose reduction or suspension is necessary.

Once adequate control of chorea has been achieved, the dose of study drug should not be increased further.

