5.2.5 Dose Reduction or Suspension

If a subject experiences a “clinically significant” adverse event (defined below)¹ that is attributed to SD-809 ER, the investigator will use his or her judgment to determine if a dose reduction or suspension is necessary. Dose adjustments should be made based on all available information including the subject’s and caregiver’s reports of adverse events and chorea control, the clinical assessment of safety and efficacy by the investigator and information from rating scales.

Dose reductions should generally occur in increments of 6 mg/day, except in the case of addition of a strong CYP2D6 inhibitor (i.e., paroxetine, fluoxetine, bupropion) or if the most recent dose increase was 12 mg/day, in which a greater dose reduction may be required. Dose reductions in this context should be reviewed with the Clinical Monitor. A dose reduction of 6 mg/day can be made by requesting that the next lowest dose level be shipped directly to the subject. Dose reductions greater than 6 mg/day should be reviewed with the Clinical Monitor. If a subject requires a dose reduction based on a telephone contact during the maintenance period, an unscheduled clinic visit should be conducted in a timely manner thereafter.

Suspension of study medication for up to one week, if warranted, is allowed.

Suspensions of study medication for adverse events must be reviewed with the Clinical Monitor before therapy is restarted. If study medication is restarted after a suspension for an adverse event, a dose reduction of 6 mg or more is permitted.

Suspensions for more than 7 days must be reviewed by the Clinical Monitor. If the subject restarts study medication within 7 days of suspension, the full dose of SD-809 ER may be resumed without titration. If subject restarts study medication greater than 7 days following a suspension, re-titration will be required.

The reason for a dose reduction or suspension must be clearly documented.

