6.3 Long Term Treatment Period

All subjects will enter the long term treatment period after Week 2, although dose adjustment may continue in Switch subjects and titration may continue in Rollover subjects.

During long term treatment, all subjects will be contacted by telephone at Week 3 and will return to the clinic on Weeks 4, 8, 15, 28 and every 13 weeks thereafter for evaluation of safety and chorea control. In addition, Rollover subjects will have an additional telephone contact at Week 5. Switch subjects will have an additional telephone contact at Week 7, to remind subjects to complete diary card before the Week 8 visit. **Subjects who have not achieved a dose level that adequately controls chorea and is well tolerated by the Week 4 visit (Switch subjects) or Week 5 telecon (Rollover subjects) should have unscheduled visits or telephone contacts in order to further adjust their dose upward or downward.** Site interactions for dose adjustment should alternate between telephone contacts and clinic visits. During long-term treatment, further dose adjustments of SD-809 ER may be made, if necessary, but not more often than weekly and in increments of 6 mg (6 mg/day or 12 mg/day after a total daily dose of 48 mg is reached). Dose adjustments should be based on all available information including the subject's and caregiver's reports of adverse events and chorea control, information from rating scales and all safety evaluations. If subjects become non-ambulatory or require more aid than an assistive device during long term treatment, they will be permitted to remain in the study.

At the end of the long term treatment period, subjects will undergo a comprehensive evaluation, including physical and complete neurological exam, safety labs and 12-lead ECG and performance of all rating scales.

6.3.1 Telephone Contacts (One week prior to Baseline visit [Switch only]; Week 3 ± 3 days [All Subjects]; Week 5 ± 3 days [Rollover only]; Week 7±3 days [Switch only])

See the Schedule of Events A and B for a detailed summary of activities.

All subjects will be contacted by telephone during Week 3 to assess adverse events, chorea control (in consultation with the subject and caregiver), concomitant medication use, evaluation of study drug dose level and adjustment, if necessary and to schedule/confirm the next visit. Following the above assessments, study medication will be re-ordered according to specified procedures.

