8.3 Safety Analyses

Safety and tolerability will be assessed throughout the study by monitoring the following parameters:

 • Adverse events (AEs) • Clinical laboratory tests • Physical examination • Vital signs • 12- lead ECGs • Epworth Sleepiness Scale (ESS) 	
 • Columbia Suicide Severity Rating Scale (C-SSRS) • Unified Huntington’s Disease Rating Scale (UHDRS) • Swallowing Disturbance Questionnaire (SDQ) • Unified Parkinson’s Disease Rating Scale (UPDRS), dysarthria item • Barnes Akathisia Rating Scale (BARS) • Hospital Anxiety and Depression Scale (HADS) • Montreal Cognitive Assessment (MoCA©)
---	--

Safety data will be summarized descriptively for the overall population and based on prior treatment [SD-809 ER or placebo (Rollover subjects) or tetrabenazine (Switch subjects)]. Descriptive statistics will be calculated for quantitative data and frequency counts and percentages will be provided for categorical data. Descriptive statistics of change-from-baseline for Rollover subjects will utilize the Baseline from Study SD-809-C-15 (C-15 Baseline) and the Baseline from the present study (C-16 Baseline), as appropriate, and will be specified in the Statistical Analysis Plan.

The nature, frequency, and severity of adverse events will be tabulated for all subjects combined and by treatment. Baseline, within study, end of study, and change-from-baseline values for clinical laboratory evaluations and vital signs will be summarized as appropriate.

Treatment-emergent adverse events and laboratory, vital sign, and ECG parameters will be summarized. In addition, change from baseline will be summarized for laboratory and vital sign parameters. Shift tables will be provided for clinical laboratory results. ECG results will be classified as normal and abnormal and summarized.

8.4 *Safety Endpoints*

The following safety endpoints will be assessed:

- Incidence of adverse events (AEs), serious AEs, severe AEs, drug related AEs, AEs leading to withdrawal during the following periods:
 - Overall
 - During titration in Rollover subjects (up to 8 weeks)
 - During dose adjustment in Switch subjects (up to 4 weeks)
 - During long term treatment
- Observed values and changes from baseline in clinical laboratory parameters (hematology, chemistry, and urinalysis)
- Observed values and changes from baseline in vital signs
- Observed values in ECG parameters and abnormal findings

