7.2 Safety Endpoints

Safety and tolerability will be assessed throughout the study by monitoring the following:

- Incidence of adverse events (AEs), serious AEs (SAEs), severe AEs, drug-related AEs, and AEs leading to withdrawal during the following periods:
 - The entire post-baseline period
 - During the Titration Period (from Day 1 to the end of Week 8) in Rollover subjects
 - During the Dose-Adjustment Period (from Day 1 to the end of Week 4) in Switch subjects
 - During the Extended Dose-Adjustment Period (from Day 1 to the end of Week 8) in Switch subjects who undergo dose adjustment between Weeks 4 and 8 (if at least 10% of Switch subjects have had a dose adjustment between Week 4 and Week 8)
 - During the Stable-Dose Period (Week 8 to end of study)
- Observed values and changes from baseline in clinical laboratory parameters (hematology, chemistry, and urinalysis)
- Observed values and changes from baseline in vital signs
- Observed values in ECG parameters and abnormal findings

- Numbers of subjects with QTcF values > 450 msec, > 480 msec, > 500 msec
- Counts and percentages for Columbia Suicide Severity Rating Scale (C-SSRS)
- Observed values and changes from baseline in the following:
 - Unified Huntington Disease Rating Scale (UHDRS)
 - Unified Parkinson's Disease Rating Scale (UPDRS) (dysarthria)
 - Barnes Akathisia Rating Scale (BARS)
 - Hospital Anxiety and Depression Scale (HADS)
 - Epworth Sleepiness Scale (ESS)
 - Montreal Cognitive Assessment (MoCA[®])
 - Swallowing Disturbance Questionnaire (SDQ)
- Duration of time to achieve a stable dose of SD-809, defined as the number of days from Day 1 until the first day at which the subject was taking the dose level they were receiving at Week 8.

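### The SAP replaces the protocol's long-term adverse event period with a Week 8 Stable-Dose Period that is not declared as a change and sets no condition on dose stability

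*SAP*

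**What the plan says.** Protocol 8.4 lists adverse event incidence for four periods: overall, Rollover titration (up to 8 weeks), Switch dose adjustment (up to 4 weeks), and "During long term treatment". Protocol 3.2 fixes the start of the last one: "the long term period of the study will be deemed to have started after two weeks of treatment even though dose adjustment may continue". Protocol 6.3 says the same operationally: "All subjects will enter the long term treatment period after Week 2". The design text in SAP section 4 also keeps the Week 2 start.

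The analysis sections of the SAP do not carry that period. The endpoint list (7.2), the period definitions (8.8) and the adverse event analyses (9.9.1) use instead "Stable-Dose Period - from Week 8 through the last dose of study drug". It applies to both cohorts, except that subjects who withdraw earlier have no such period. SAP 8.10, which records changes to protocol-specified analyses, names only two: the compliance range, and the move of total maximal chorea and total motor score to efficacy.

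The dose may still move after Week 8. For Rollover subjects Protocol 5.2.3 states: "Additional dose adjustments may be made after week 8 if clinically indicated". SAP section 4 also allows it. Protocol 5.2.5 adds: "If subject restarts study medication greater than 7 days following a suspension, re-titration will be required".

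**The concern.** Objective 1 covers both titration and maintenance, so the labels on the adverse event tables matter. A reader of the study report will take a stable-dose table to describe tolerability once the dose has settled. The definition looks only at the calendar. SAP 7.2 also defines time to stable dose by whatever dose is taken at Week 8 and ignores later changes. Events provoked by a dose increase or a restart after Week 8 would therefore be read as events on a settled dose. Separately, a safety endpoint period that the protocol names would be missing from the report, with no entry in the section where a reader looks for such changes.

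**Working it through.** **Period boundary.** Protocol: long-term treatment starts after Week 2, Day 14. SAP: the Stable-Dose Period starts at Week 8, Day 56. The difference is 56 − 14 = 42 days. If nobody leaves before Week 8, the person-time moved out of the later period is at most:

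- all subjects: 116 × 42 / 365.25 = 13.3 person-years
- Rollover: 80 × 42 / 365.25 = 9.2
- Switch: 36 × 42 / 365.25 = 4.1

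**Dose path.** Inputs:

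- Rollover start 6 mg/day (Protocol 5.2.3)
- steps of 6 mg/day, at most weekly, or 6 or 12 mg/day once 48 mg/day is reached (5.2.1, 5.2.3)
- maximum 72 mg/day, or 42 mg/day with a strong CYP2D6 inhibitor (5.2.1)
- Switch starts from 6 to 48 mg/day (Table 1)

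Check against the plan's own figure: 6 mg in the first week plus one step at Week 1 gives 12 mg/day in the second week. Protocol 3.2 expects Rollover subjects to be at 12 mg/day by two weeks, so the model agrees.

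For a starting dose s and an increase at every permitted week:

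- first dose above 48 mg: week (54 − s)/6
- 72 mg: week (48 − s)/6 + 2 with 12 mg steps, or + 4 with 6 mg steps

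| Start (mg/day) | First above 48 mg | 72 mg, 12 mg steps | 72 mg, 6 mg steps |
|---|---|---|---|
| 6 (all Rollover; lowest Switch) | Week 8 | Week 9 | Week 11 |
| 12 | Week 7 | Week 8 | Week 10 |
| 24 | Week 5 | Week 6 | Week 8 |
| 36 | Week 3 | Week 4 | Week 6 |
| 48 | Week 1 | Week 2 | Week 4 |

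The Rollover path in full is 6, 12, 18, 24, 30, 36, 42, 48 mg (Week 7), then 54 or 60 mg at Week 8. If doses change only at the scheduled contacts (Weeks 1 to 5 and Week 8), the subject enters Week 8 on 36 mg and leaves it on 42 mg. Either way, every step above 48 mg falls at or after Week 8. One edge case: with a first dose on Day 1, the eighth increase falls on Day 57, so a Week 8 visit late in its ±3 day window could follow it. Hence about Week 8.

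**Other changes after Week 8.** Schedule of Events B marks dose adjustment at the Week 8 visit itself for Rollover subjects, so events following that scheduled step fall in the Stable-Dose Period. Re-titration to a dose d takes (d − 6)/6 weekly steps if it restarts at 6 mg, which is an assumption because Protocol 5.2.5 gives no restart dose. For 48 mg that is 7 steps. Only the part that runs past Week 8 is labelled stable.

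**Does any planned table separate these events?** SAP 9.5 lists dose changes by subject and 9.8 summarises dose by visit; neither is linked to adverse events. SAP 9.9.1 tabulates events by calendar period, and its exposure-adjusted rates are by cohort and study. It also tabulates events that led to dose reduction or suspension, but none by whether they followed an increase or a restart.

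**The case against.** The case on the other side is substantial, and much of it stands.

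- The 8-week cap on Rollover titration is the protocol's own (8.4); the SAP copies it. Protocol 6.2 and 6.3.2 also treat the end of titration, Week 8 for Rollover subjects, as the point from which the long-term dose is normally continued.
- The protocol's after-Week-2 period contains even more titration than the SAP's. Starting at Week 8 takes the Weeks 2 to 8 events out of the later period.
- The new period is openly defined and used throughout the SAP. Only the entry in 8.10 is missing.
- The dose path is a ceiling. Increases stop once chorea is controlled, and subjects on strong CYP2D6 inhibitors cannot go above 42 mg/day.

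A reader might infer three stronger things that the documents do not support. First, that the SAP's substitution causes titration and maintenance events to be mixed: the protocol's own period mixes them too. Second, that titration event rates throughout the trial omit the top third of the dose range, (72 − 48)/72 = 33%: Switch subjects starting on 12 mg or more can exceed 48 mg before Week 8. Third, that long-term events go unreported: the Entire Treatment Period tables keep them all, and Rollover events in Weeks 2 to 8 appear in the titration tables.

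What the objection does not remove is the absent endpoint. Incidence tables count a subject once per preferred term within a period, so after-Week-2 incidence cannot be recovered by adding the other tables. Nor does it supply a stability condition for a period named Stable-Dose.

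**Conclusion.** The point holds in a limited form, with two faults. An adverse event period specified in Protocol 8.4 is omitted without an entry in SAP 8.10; the shift is 42 days and at most 13.3 person-years, assuming full planned enrolment and no loss before Week 8. The replacement also carries a label that its rule does not deliver. Under the protocol's weekly steps, any escalation above 48 mg/day in Rollover subjects (about 80 of 116, 69%), and in Switch subjects starting on 6 mg, comes at about Week 8 or later and is tabulated as stable-dose. The same applies to events after any other later increase, and to re-titration past Week 8.

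The 69% is the share of planned subjects to whom the dose limit applies, not the share who will escalate. The documents do not say how many subjects will go above 48 mg, change dose after Week 8 or be re-titrated, so the effect on event rates cannot be sized from them.

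**What to change.** 1. Report treatment-emergent adverse events by cohort for the protocol's long-term period (onset after Week 2), or state in SAP 8.10 that it has been replaced and why. This restores or accounts for the endpoint; it does not by itself separate titration events from maintenance events.
2. Rename the Stable-Dose Period the Post-Week-8 Period. From the dosing data already listed under SAP 9.5, tabulate its events and person-time separately for time within a pre-specified interval (for example 14 days) after a dose increase or a restart, and for time on an unchanged dose. State where time during a suspension or after a reduction is counted. Repeat with one alternative interval as a sensitivity check.

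The cost is SAP wording and a few extra descriptive tables from data already collected. The interval is arbitrary, which is why it should be fixed beforehand and varied once. No visit, assessment or dosing rule changes.

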8.9 Analysis Visit Windows

For efficacy and safety by-visit analyses, data collected at post baseline scheduled visits will be included using their nominal visit. Data collected at early termination, end of treatment, and unscheduled visits will be assigned to a visit window as described below. All scheduled visits will be assigned a target study day; for the determination of target days, weeks will be assumed to have 7 days. Thus, Week 4 would have a target day of $4 \times 7 = 28$ days. For each visit, a visit window will be assigned so that anything from the midpoint to the prior target day to the midpoint to the following target day will be assigned to that visit window as shown in Table 3 below. The following rules concerning visit windows and selecting records for analysis will be used:

1. Scheduled visit has precedence.

2. If there are multiple records of the same scheduled visit, the record closest to the target day will be used for analysis. If two records are equidistant, then the earlier one will be used.
3. For a given visit, if there is no data from a scheduled visit, data from an unscheduled visit that occurs in the visit window will be used for analysis.

Table 3: Analysis Visit Window

| Visit | Target Day | Visit Window |
|-----------------------------|------------|--------------|
| Screening | -5 | (--, -5) |
| Screening Telephone Contact | -2 | (-4, -2) |
| Baseline | -1 | (-1, -1) |
| Week 1 | 7 | (1,10) |
| Week 2 | 14 | (11-17) |
| Week 3 | 21 | (18, 24) |
| Week 4 | 28 | (25, 31) |
| Week 5 | 35 | (32, 38) |
| Week 7 | 49 | (39, 52) |
| Week 8 | 56 | (53, 80) |
| Week 15 | 105 | (81, 150) |
| Week 28 | 196 | (151, 241) |
| Week 41 | 287 | (242, 332) |
| Week 54 | 378 | (333, 423) |
| Week 67 | 469 | (424, 514) |
| Week 80 | 560 | (515, 605) |
| Week 93 | 651 | (606, 697) |
| Week 106 | 742 | (698, 787) |
| Week 119 | 833 | (788, 879) |
| Week 132 | 924 | (880, 970) |
| Week 145 | 1015 | (971, 1060) |
| Week 158 | 1106 | (1061, 1152) |
| Week 171 | 1197 | (1153, --) |

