6.5 Unscheduled Visit(s)

See the Schedule of Events A and B for a detailed summary of activities.

Unscheduled visits may be performed for Dose Adjustment or evaluation of intercurrent events. Visits for Dose adjustment should focus on evaluating chorea control, adverse events

and adjusting the dose of study medication, if indicated. Additional safety measures may be performed at the investigator's discretion.

For unscheduled clinic visit(s) conducted during the course of the study, the following activities should be performed:

- Assessment of adverse events, chorea control (in consultation with the subject and caregiver), and concomitant medications
- Vital signs and weight
- Unified Huntington's Disease Rating Scale (UHDRS)
 - Motor
- Evaluation of study drug dose level and adjustment, if necessary

The following assessments are at the Investigator's discretion and should be performed if indicated:

- 12-lead ECG
- Clinical laboratory tests: serum chemistry, hematology, and urinalysis
- Single PK Blood Sample (for Unscheduled Visits due to SAE, if within 48 hours, if possible)
- Hospital Anxiety and Depression Scale (HADS)
- Columbia Suicide Severity Rating Scale (C-SSRS): Since Last Visit version
- Unified Parkinson's Disease Rating Scale (UPDRS): dysarthria item
- Barnes Akathisia Rating Scale (BARS)
- Epworth Sleepiness Scale (ESS)
- Swallowing Disturbance Questionnaire (SDQ)

- Re-order study medication

For unscheduled telephone visit(s) needed during the course of the study, the following activities should be performed:

- Assessment of adverse events, chorea control and concomitant medications in consultation with the subject and caregiver.
- Evaluation of study drug dose level and adjustment, if necessary (at the Investigator's discretion)

- Re-order study medication (at the Investigator's discretion) (See Operations Manual for further details)

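### SAP Table 3 gives telephone contacts their own windows and departs from its midpoint rule, so early-termination or unscheduled readings on Days 18-24 and 32-52 cannot enter Week 4 or Week 8

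*SAP*

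**What the plan says.** SAP 8.9 keeps scheduled post-baseline data at their nominal visit. Other data are windowed: "Data collected at early termination, end of treatment, and unscheduled visits will be assigned to a visit window as described below". Targets are simple multiples: "for the determination of target days, weeks will be assumed to have 7 days". Boundaries follow the midpoint rule: "anything from the midpoint to the prior target day to the midpoint to the following target day will be assigned to that visit window". A scheduled record always takes precedence; otherwise, "if there is no data from a scheduled visit, data from an unscheduled visit that occurs in the visit window will be used for analysis".

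There is a single table, Table 3, for both cohorts and all by-visit analyses. Its early rows are Week 1 (1-10), Week 2 (11-17), Week 3 (18-24), Week 4 (25-31), Week 5 (32-38), Week 7 (39-52) and Week 8 (53-80).

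Several of these rows are not clinic visits. Protocol 6.3 says that "all subjects will be contacted by telephone at Week 3", that "Rollover subjects will have an additional telephone contact at Week 5", and that "Switch subjects will have an additional telephone contact at Week 7, to remind subjects to complete diary card before the Week 8 visit". Switch subjects have no Week 5 contact and Rollover subjects have no Week 7 contact. Week 2 is a telephone contact for Switch and Week 1 is one for Rollover (Protocol 6.2.1 and 6.2.2). The schedules of events place no rating scale, vital sign or ECG at any of these contacts.

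Protocol 6.5 opens its list for unscheduled clinic visits with "For unscheduled clinic visit(s) conducted during the course of the study, the following activities should be performed". The list includes vital signs, weight and UHDRS Motor; the ECG and several other scales are discretionary. The early-termination visit (Protocol 6.3.3) includes all the scales, an ECG and orthostatic readings.

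**The concern.** A window in a by-visit analysis exists to bring an off-schedule value to the nearest visit at which that value was due. A window centred on a telephone call does the opposite: it diverts the value to a row that has no scheduled data to join. In Days 18-24 and 32-52 a rating can come only from an unscheduled clinic visit or from early termination. Those subjects are a selected group, and their values are kept out of the Week 4 and Week 8 summaries.

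Week 8 is where this counts most. SAP 9.7 analyses the cohorts separately through Week 8 and uses Week 8 as the reference for later change. SAP 9.9.5 summarises ECG parameters and the QTcF threshold counts at Screening and Week 8, with earlier visits added only for subjects on citalopram or escitalopram. SAP 9.9.3 summarises orthostatic differences at Baseline and Week 8. An ECG or orthostatic reading from an early termination on Day 45 is given to Week 7, so it would appear in listings but in none of those tables.

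**Working it through.** **Inputs.** Targets are 7 x week number. Windows come from SAP Table 3. Contact types come from Protocol 6.2.1, 6.2.2 and 6.3 and the schedules of events.

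**1. Reproducing Table 3.** Boundary = (target + next target)/2. Of the 19 post-baseline boundaries, 14 agree with the table, for example Week 4/5: (28+35)/2 = 31.5; Week 7/8: (49+56)/2 = 52.5; Week 8/15: (56+105)/2 = 80.5. Five do not:

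| Boundary | Midpoint rule | Table 3 | Difference (days) |
|---|---|---|---|
| Week 5/7 | (35+49)/2 = 42 | 38.5 | -3.5 |
| Week 93/106 | (651+742)/2 = 696.5 | 697.5 | +1 |
| Week 119/132 | (833+924)/2 = 878.5 | 879.5 | +1 |
| Week 132/145 | (924+1015)/2 = 969.5 | 970.5 | +1 |
| Week 158/171 | (1106+1197)/2 = 1151.5 | 1152.5 | +1 |

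No other list of targets gives both early windows. Adding a Week 6 target (Day 42) yields Week 5 = 32-38 but Week 7 = 46-52. Switch contacts alone yield Week 7 = 39-52, since (28+49)/2 = 38.5, but no Week 5 row. Rollover contacts alone yield Week 5 = 32-45.

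**2. Effect of the Week 5/7 slip alone.** Correcting it, with the tie at Day 42 going to the earlier visit, gives Week 5 = 32-42 and Week 7 = 43-52. Days 39-42 move between two rows that hold no scheduled ratings. Nothing moves into Week 4 or Week 8.

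**3. Where Days 1-80 go.** Weeks 3, 5 and 7 take 7 + 7 + 14 = 28 days. Week 4 takes 7 and Week 8 takes 28, together 35. Weeks 1 and 2 take 10 + 7 = 17. The sum is 28 + 35 + 17 = 80. These are counts of calendar days, not of ratings.

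**4. Asymmetry at Week 8 (Day 56).** A reading on Day 52 is 56 - 52 = 4 days early and is refused. A reading on Day 80 is 80 - 56 = 24 days late and is accepted. The Week 7 row causes this.

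**5. The SAP's rule applied to clinic visits only**, ties to the earlier visit:

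| Cohort | Boundaries | Windows |
|---|---|---|
| Switch | (7+28)/2 = 17.5; (28+56)/2 = 42; (56+105)/2 = 80.5 | Week 1 = 1-17; Week 4 = 18-42; Week 8 = 43-80 |
| Rollover | (14+28)/2 = 21; (28+56)/2 = 42; (56+105)/2 = 80.5 | Week 2 = 1-21; Week 4 = 22-42; Week 8 = 43-80 |

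Days 43-52 move to Week 8 and Days 32-42 to Week 4. Days 18-24 move to Week 4 for Switch; for Rollover, Days 18-21 move to Week 2 and Days 22-24 to Week 4.

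**6. Who is affected after precedence.** A subject seen on Days 32-42 will usually have a scheduled Week 4 rating already, so nothing changes. The main gain is Days 43-52 with no Week 8 visit, then Days 18-24 (Switch) or 22-24 (Rollover) with no Week 4 visit.

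**7. Illustration (assumption; the documents give no such count).** Suppose 3 to 8 of about 116 subjects leave during Days 32-52, evenly over those 21 days. Ten of the 21 days (43-52) belong to Week 8: 3 x 10/21 = 1.4 and 8 x 10/21 = 3.8, or about 1 to 4 subjects.

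**The case against.** The case for leaving Table 3 nearly as it is has substance. Scheduled data keep their nominal visit, so most ratings never meet a window. Rollover titration may run through Week 8, and unscheduled contacts are the protocol's route for continuing it. A visit on Day 45 may therefore be ordinary titration, and calling it Week 8 mixes dose stages at a reference visit. The SAP plans no formal testing and no imputation of missing endpoints. Withdrawals with reasons (9.1) and adverse events leading to dose reduction, suspension or withdrawal (9.9.1) are tabulated independently of Table 3. TMC is repeated on scheduled visits only.

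Much of this limits the size of the problem. It does not justify windows centred on telephone calls. The TMC repeat drops the displaced values rather than placing them, and no such repeat is planned for other measures. Adverse-event tables do not replace a missing ECG or orthostatic reading.

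Some stronger readings are tempting but unsupported:

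- That these ratings can never enter Week 4 or Week 8. They can on Days 25-31 and 53-80 if the scheduled rating is missing.
- That the midpoint slip causes the exclusion. Step 2 shows that it does not.
- That everyone leaving in Days 32-52 is lost from Week 8. Days 32-42 lie nearer to Week 4 or are tied with it.
- That the share of days in telephone rows measures the share of data affected.
- That the telephone rows will be displayed as ordinary visits. No table shells are in the documents.

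**Conclusion.** The point stands as a limited defect with a cheap correction. Table 3 contradicts its stated rule at Week 5/7 by 3.5 days and at four later boundaries by one day. More importantly, telephone contacts hold windows for measurements not scheduled at them, so early-termination and unscheduled readings on Days 18-24 and 32-52 cannot enter Week 4 or Week 8. The clearest consequence is for ECG and orthostatic readings from early terminations on Days 43-52, which would reach no by-visit table.

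The number of subjects cannot be derived from the documents. It is likely small, and subjects who have the scheduled rating are unaffected. Change-from-Week-8 results would move little, because a subject who has terminated contributes no later on-treatment visit. The conclusion assumes that Table 3 applies to every by-visit assessment, as SAP 8.9 is worded.

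**What to change.** Define windows per cohort and per assessment, using only visits at which that assessment is scheduled, by the SAP's own midpoint rule with ties to the earlier visit.

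- **Scales and vital signs:** Switch Week 1 = Days 1-17, Week 4 = 18-42, Week 8 = 43-80; Rollover Week 2 = Days 1-21, Week 4 = 22-42, Week 8 = 43-80. MoCA and the UHDRS cognitive tests, first scheduled after baseline at Week 4 in SAP Tables 1 and 2, need their own entry.
- **Laboratory tests, ECG and orthostatic readings:** proceed likewise. For orthostatic readings, and for ECG in most subjects, Week 8 is the only scheduled post-baseline visit before End of Treatment. The midpoint rule then fixes no outer limits and the SAP must state them; the window should at least cover Days 43-80.
- **Precedence:** keep it as written.
- **Telephone contacts:** show no scale rows for them. If such rows are kept for items collected by telephone, correct the Week 5/7 boundary.
- **Later boundaries:** end Weeks 93, 119, 132 and 158 on Days 696, 878, 969 and 1151, and start the following windows one day later.

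The cost is SAP text and programming; no new data are needed. The downside is that newly admitted values can lie about two weeks from the nominal visit (Day 43 is 13 days before Day 56; Day 42 is 14 days after Day 28), and some Rollover values labelled Week 8 may precede the end of titration. The planned scheduled-visits-only repeat for TMC remains as the sensitivity check.
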